6.6.2 Adverse Events

Adverse Events (AE) will be collected from time of the first dose throughout the treatment period and including the Off-treatment phase (see section 6.2.3 for the phase definition). SAEs will be recorded from the time of informed consent.

After the imputation of AE start date and AE end date as described in section 7.3, AEs will be assigned to the period where they start according to the following algorithm:

If both the start date and start time of an AE are known, then:

- If the AE starts prior to the first dose of IP, then the AE will be assigned to the Baseline phase
- If the AE starts on or after the first dose of IP through 7 days after the date of the last dose of IP (inclusive), then the AE will be assigned to the On-treatment phase,

TPCA025 Version 2 (based on TPQA036 Version 2) Original:

Effective Date: 27th August 2017 Prior Effective Date: 21st December 2016

Distribution:

Sponsor:	AstraZeneca AB	Protocol/CIP Number:	D7550C00003
CIL Project Number:	40343		

• If the AE starts after the date of last dose of IP + 7 days (not inclusive), then the AE will be assigned to the Off-treatment phase.

If only the start date of an AE is known, and the start time of the AE is unknown, then:

- If the AE starts prior to the date of the first dose of IP, then the AE will be assigned to the Baseline phase,
- If the AE starts on or after the date of the first dose of IP through 7 days after the date of last dose of IP (inclusive), then the AE will be assigned to the On-treatment phase,
- If the AE starts after the date of last dose of IP + 7 days (not inclusive), then the AE will be assigned to the Off-treatment phase.

If the start date of an AE is completely missing, the AE should be assigned as follow:

- If the end-date is known:
 - If the end-date is before the date of first study IP then the AE will be assigned to the Baseline phase
 - If the end-date is on or after the date of first IP, no assignation can be done.
- If the end-date is completely missing no assignation can be done

The way the SAEs will be assigned to a specific period will be different for the first IA and second IA/final analysis.

First IA considerations

After the AE allocation to corresponding study phase, also the AE seriousness part of the event will be allocated to the corresponding study phase by means of the date in which the AE becomes serious.

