After the imputation of the AE becomes serious as described in section 7.3, the SAE will be assigned to the period where it starts according to the following algorithm:

- If the date in which the AE becomes serious is prior to the date of the first dose of IP, then the SAE will be assigned to the Baseline phase,
- If the date in which the AE becomes serious is on or after the date of the first dose of IP through 7 days after the date of last dose of IP (inclusive), then the SAE will be assigned to the On-treatment phase,
- If the date in which the AE becomes serious is after the date of last dose of IP + 7 days, then the SAE will be assigned to the Off-treatment phase.

If the date in which the AE became serious is completely missing, the SAE will be assigned according to the AE start date and time.

The SAE assignation is used only to identify cases in which the AE starts as Non-serious in the On-treatment phase and becomes Serious in the Off-treatment phase. In cases like these, the AE will be reported as one single AE in the listings, but it will be summarized as one non-serious AE in the On-treatment tables and one SAE in the Off-treatment tables.

TPCA025 Version 2 (based on TPQA036 Version 2) Original:

Copy:

Effective Date: 27th August 2017 Prior Effective Date: 21st December 2016

Distribution:

Sponsor:	AstraZeneca AB	Protocol/CIP Number:	D7550C00003
CIL Project Number:	40343		

Second IA and final analysis considerations

If the AE started in the on-treatment phase and became serious in the off-treatment phase, the AE will be considered as serious from the start, i.e. in the on-treatment phase as well. The AE will be reported as one single record in the listing.

A drug-related AE is defined as any AE with a reasonable possibility of causal relationship to study treatment as assessed by the investigator or with missing assessment of the causal relationship.

The coding dictionary for this study will be the Medical Dictionary for Regulatory Activities (MedDRA) version 20.0 or higher.

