8.10 Interim analysis

Two administrative interim analyses will be conducted. The first one is planned after at least 45 patients have performed their CFVR measurement at Visit 4 and the second after at least 100 patients have performed their CFVR measurement at Visit 4. The variables for the analyses will be:

- CFVR
- LV Global Longitudinal Strain (GLS) at rest
- LVEF
- Carotid-femoral pulse wave velocity and brachial pulse wave analysis: Augmentation index, Carotid-femoral pulse wave velocity, Pulse pressure amplification and Central pulse pressure
- Cardiovascular Biomarkers: hsCRP (High-sensitivity C-Reactive Protein), NT-proBNP (N-Terminal Prohormone of Brain Natriuretic Peptide)

These analyses will not have any impact on the overall type-1 error because no changes will be made to the trial based on the outcome of the analyses. The purpose with the interim analyses is to trigger external activities not connected to the trial. Both interim analyses will be performed by study independent personnel.

An Interim Analysis Charter will define the deliverables and procedures for the provision and communication of the planned interim analyses described in the statistical analysis plan. The maintenance of the blind for the Study Team is also addressed. Further details will be given in the Interim Analysis Charter.

The two interim analyses will be focused on to:

Description of the study population:

- Description and comparison of the active groups and the placebo group
- Estimation of the effect on safety variables

The cut-off date for second IA will be determined by the study team.

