8.10.1 Description of study population

In order to characterize the population used for the interim analyses, subject disposition, important protocol deviations and analysis sets will be presented.

Distribution:

Original:

Copy:

TPCA025 Version 2 (based on TPQA036 Version 2)

Sponsor:	AstraZeneca AB	Protocol/CIP Number:	D7550C00003
CIL Project Number:	40343		

Subject disposition

Subject disposition - Cohort 4w treatment and Cohort 12w treatment - and analysis sets will be summarized.

Additionally, for the second IA, the demographic characteristics will be presented by cohort of patients and will include Age (years), Age group (<50; >=50 -<65; >=65 years), sex, race, ethnicity and country.

Important protocol deviations

IPDs are described and classified section 8.2.

Classified IPDs will be assessed for the Efficacy Analysis Set. The number and percentage of subjects with at least one IPD will be summarized globally and for each category, by treatment group and total.

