8.10.3 Estimate the effect on safety variables

The effect on safety variables will be presented using the Safety Analysis Set by treatment group. Below a detailed description of the summaries that will be used for the purpose:

Adverse Events

AEs will be assigned to the study phases as described in section 6.6.2.

Original:

Copy:

TPCA025 Version 2 (based on TPQA036 Version 2) Effective Date: 27th August 2017 Prior Effective Date: 21st December 2016

Sponsor:	AstraZeneca AB	Protocol/CIP Number:	D7550C00003
CIL Project Number:	40343		

Unless otherwise specified, AEs and SAEs will be summarized using the Safety Analysis Set by treatment group and by cohort of patients. Percentages will be based on the total numbers of subjects in the treatment group.

Subjects with multiple events in the same category will be counted only once in that category. Subjects with events in more than 1 category will be counted once in each of those categories.

Only On-treatment phase up to visit 4 at the first IA and up to the cut-off date at the second IA will be reported for each summary table.

The following summary tables will be reported:

An overview table for all the AEs, only for the On-treatment phase.

The number and percentage of subjects with any AEs for each SOC and PT, only for the On-treatment phase.

The number and percentage of subjects with any SAEs for each for each SOC and PT, only for the On-treatment phase.

The following table will be reported for the first IA only:

The number and percentage of subjects with any non-serious AEs only for the On-treatment phase and only for those categories which show more that 5% of frequency, globally and for each PT.

Additionally, for the second IA, the following summary tables will be reported:

The number and percentage of subjects with AEs with outcome of death for each SOC and PT, only for the On-treatment phase.

The number and percentage of subjects with AEs leading to treatment discontinuation for each SOC and PT in the On-treatment phase.

The following listings will be reported for the second IA:

Listings will also be presented by subject for all AEs using the Safety Analysis Set.

Listing of SAEs will also be presented for enrolled but not randomized subjects and for subjects who were not exposed to treatment.

Laboratory test results for haematology, coagulation and clinical chemistry

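### At the first interim, an adverse event that turns serious or fatal more than 7 days after last dose is tabulated only as non-serious, because the Off-treatment tables that SAP 6.6.2 relies on are not planned in SAP 8.10.3

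*SAP*

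**What the plan says.** SAP 6.6.2 defines the On-treatment phase so that it runs past the last dose: an event starting on or after first dose "through 7 days after the date of the last dose of IP (inclusive), then the AE will be assigned to the On-treatment phase". Later starts are Off-treatment.

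The same section has two rules for an event that starts on treatment and becomes serious in the Off-treatment phase. Under the heading for the first interim, "it will be summarized as one non-serious AE in the On-treatment tables and one SAE in the Off-treatment tables". Under the heading for the second interim and the final analysis, "the AE will be considered as serious from the start".

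SAP 8.10.3 then lists the interim outputs. Its general limit is: "Only On-treatment phase up to visit 4 at the first IA and up to the cut-off date at the second IA will be reported". At the first interim this leaves an AE overview, AEs by SOC and PT, SAEs by SOC and PT, and a table planned for that look only: "The number and percentage of subjects with any non-serious AEs only for the On-treatment phase", restricted to categories above 5% frequency. The fatal-AE and AE-discontinuation tables are assigned to the second interim. So are the listings: "The following listings will be reported for the second IA". No Off-treatment table and no all-deaths table is named for either interim, although shells for both exist in SAP section 12.

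Protocol 8.5.6 places an unblinded safety review committee (SRC) at the first interim, with access to AEs, SAEs and safety laboratory data. SAP 8.10 adds: "An Interim Analysis Charter will define the deliverables and procedures for the provision and communication of the planned interim analyses".

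**The concern.** The first-interim rule in 6.6.2 makes sense only if two sets of tables are produced, one for each phase. SAP 8.10.3 produces one. An event that begins on treatment and becomes serious, or fatal, more than 7 days after last dose loses its serious status in the only tables planned. It can even be counted in the frequent non-serious table if its preferred term passes 5%. Section 6.6.2 also says the event appears once in the listings, but no AE listing is planned for this look.

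SAEs and deaths from events that start after the tabulated window have no planned first-interim AE table at all.

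At stake is the by-arm count of serious and fatal events at the one interim for which the protocol names an SRC review, in patients with a recent acute coronary syndrome.

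**Working it through.** **Rules set side by side, for an event that starts on treatment and turns serious more than 7 days after last dose**

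| Look | Rule in SAP 6.6.2 | Tables in SAP 8.10.3 / 8.8.2 | How the event shows |
|---|---|---|---|
| First interim | Non-serious On-treatment, SAE Off-treatment | On-treatment only, no AE listing | Non-serious only |
| Second interim | Serious from the start | On-treatment to the cut-off, plus AE listing | Serious |
| Final | Serious from the start | Both phases, deaths, AE listing | Serious |

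The mismatch is confined to the first row.

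**Size of the untabulated window, 4-week completer**

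Inputs:
- Last dose at Visit 4, scheduled Day 28, window ±3 days (Protocol Table 1).
- Visit 5 at 28 days after last dose, ±4 days (Protocol 1.4 and Table 1).
- AEs collected from first dose through follow-up (Protocol 6.3.1).
- On-treatment phase ends 7 days after last dose (Protocol 8.5.3, SAP 6.2.3).

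The plan's own figure first. SAP Table 3 schedules Visit 5 at Day 56 for the 4-week cohort and Day 112 for the 12-week cohort: 28 + 28 = 56 and 84 + 28 = 112. Both reproduce.

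The limit at Visit 4 can be read in two ways.

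- Reading 1, the On-treatment phase keeps its 7-day tail. Shown: 28 + 7 = 35 days. Not shown: 56 − 35 = 21 days. Share: 21/56 = 37.5%.
- Reading 2, the tables stop at Visit 4. Shown: 28 days. Not shown: 56 − 28 = 28 days. Share: 28/56 = 50%.

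With both visit windows, Visit 4 falls on Day 25 to 31 and follow-up lasts 24 to 32 days. Total collection time is 25 + 24 = 49 to 31 + 32 = 63 days.

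- Reading 1: 24 − 7 = 17 to 32 − 7 = 25 days. Lowest share 17/(31 + 24) = 17/55 = 31%. Highest share 25/(25 + 32) = 25/57 = 44%.
- Reading 2: 24 to 32 days. Lowest share 24/55 = 44%. Highest share 32/57 = 56%.

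At the second interim the Off-treatment days of reading 1 (nominally 21) still have no by-arm table, but the planned AE listing covers them.

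**The case against.** The strongest reply is that this is a display choice at an administrative look that is probably over. The first interim is triggered by Visit 4, and its efficacy and laboratory outputs also stop there, so a common Visit 4 window gives both cohorts the same exposure. SAP version 7.0 is dated 18 May 2020 and speaks of COVID-19 phone visits in the past tense, so the first interim has very likely been run and the second may have been. The sponsor already uses the better seriousness rule from the second interim on. Individual SAEs are reported within 24 hours (Protocol 6.4), and the final tables cover both phases and all deaths. The split-rule case is also narrow, and no frequency is given for it.

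Most of this stands. It lowers the severity, and it supports keeping the Visit 4 cut for non-serious events. It does not reconcile the two sections: 6.6.2 directs the serious count to tables that 8.10.3 leaves out.

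Three stronger readings are tempting, and the documents do not support them.

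- A reader might infer that fatal events are invisible at the first interim. Death is an SAE criterion (Protocol 6.2), so an event that meets any SAE criterion within the tabulated window enters the planned SAE table. In addition, "subject disposition, important protocol deviations and analysis sets will be presented", and the disposition summary may show a death as a reason for leaving the study.
- A reader might infer that the SRC was denied these events. The Interim Analysis Charter governs deliverables and is not supplied, so it may add SRC outputs. What the SRC received is unknown.
- A reader might take 37.5% or 50% as the share of events, or of the whole safety database, that is lost. The figures are collection days for 4-week completers whose Visit 5 precedes the cut-off.

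**Conclusion.** The point holds as a minor inconsistency. Followed as written, the first-interim rules show an on-treatment event that becomes serious or fatal more than 7 days after last dose only as non-serious, and they leave SAEs and deaths from events starting after the cut out of every planned AE table at that look.

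The untabulated time per eligible 4-week completer is nominally 21 of 56 days (37.5%), range 17 to 25 days (about 31 to 44%), if the 7-day tail is kept. It is 28 of 56 days (50%), range 24 to 32 days (about 44 to 56%), if the tables stop at Visit 4. This assumes last dose at Visit 4 and follow-up complete before the cut-off. The documents give neither an event rate nor the number of such patients, so the number of misclassified or missing events cannot be estimated.

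The final analysis, the second-interim seriousness rule and expedited reporting are unaffected.

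**What to change.** In SAP 6.6.2, apply the rule already written for the second interim and final analysis to the first interim as well, so that an on-treatment event that later becomes serious is counted as serious from its start.

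In SAP 8.10.3, tabulate SAEs, AEs with outcome of death and all deaths by arm and cohort for all data to the interim cut-off, On- and Off-treatment separately. Shells 14.3.2.13 and 14.3.2.14, 14.3.3.1 and 14.3.3.2, and 14.3.4.1 and 14.3.4.2 serve without redesign. The Visit 4 cut may stay for non-serious events.

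If the first interim has been run, use the SAE and death tables at the second interim if that is still ahead. Reproducing them for the first cut-off is optional.

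The cost is SAP wording and a little programming. No new data are needed and type-1 error is not affected. Follow-up would differ between the 4-week and 12-week cohorts in these tables, which the by-cohort display makes visible.

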9. COMPUTER SOFTWARE

All analyses will be performed by using Version 9.1.3 or later of SAS® software. All summary tables and data listings will be prepared utilising SAS® software.

SF-36 scoring will be performed by using PRO CoRE Software 1.5.

The standard operating procedures (SOPs) of will be followed in the creation and quality control of all data displays and analyses.

11. APPENDICES

Appendix 1 Variable definitions

Assessment of variable not already explicated in the text are reported below:

Age will be calculated as the informed consent date minus the date of birth divided by 365.25 [Age=(ICF Date-DOB)/365.25].

Age group will be displayed for the following 4 categories: <50; >=50 -<65; >=65 years.

Body mass index (BMI; kg/m2) is calculated as: weight (kg) / [height (m)]², rounded to two decimal places.

BMI group will be displayed for the following 3 categories: Normal <25; Overweight >=25-<=30; Obese >30 kg/m2.

Weight will be displayed in kilograms (kg), and height will be displayed in centimetres (cm).

Weight group will be displayed for the following 4 categories: <70; >=70- <=90; >90 kg.

Distribution:

Original:

Copy:

TPCA025 Version 2 (based on TPQA036 Version 2) Effective Date: 27th August 2017 Prior Effective Date: 21st December 2016

Sponsor:	AstraZeneca AB	Protocol/CIP Number:	D7550C00003
CIL Project Number:	40343		

Appendix 2 Statistical analysis and programming details

Mixed Model with Repeated Measures (MMRM) – primary and first secondary endpoints (change at visit 4 and 4c on Creatinine normalized uLTE₄):

The SAS code used to implement this test will be similar to that shown below:

PROC MIXED data=dataset COVTEST NOCLPRINT METHOD=REML; CLASS Trt Mi Subject visit; MODEL Ch=Trt visit trt*visit MI Base / SOLUTION ddfm=KR; REPEATED Visit / TYPE=SP(POW)(awtarget) SUB=Subject; LSMESTIMATE trt*visit 'change at week X - AZD5718 vs placebo' 0 -1 0 0 1 0 / lower cl testvalue= -1.609437912 /* corresponding to ln(0.2) */; RUN;

Where awtarget is the expected day of visit.

Mixed Model with Repeated Measures (MMRM) – second and third secondary endpoints (change at visit 4 and 4c on CFVR):

The SAS code used to implement this test will be similar to that shown below:

PROC MIXED data=dataset COVTEST NOCLPRINT METHOD=REML; CLASS Trt Mi Subject visit; MODEL Ch=Trt visit trt*visit MI Base / SOLUTION ddfm=KR; REPEATED Visit / TYPE=SP(POW)(awtarget) SUB=Subject; LSMESTIMATE trt*visit 'change at week X - AZD5718 vs placebo' -1 0 1 0/ upper cl; RUN;

Where awtarget is the expected day of visit.

Mixed Model with Repeated Measures (MMRM) – change at visit 4 and 4c on Other secondary variables, all exploratory variables and cardiovascular biomarkers:

The SAS code used to implement this test will be similar to that shown below:

PROC MIXED data=dataset COVTEST NOCLPRINT METHOD=REML; CLASS Trt Mi Subject visit; MODEL Ch=Trt visit trt*visit MI Baseline / SOLUTION ddfm=KR; REPEATED Visit / TYPE=SP(POW)(awtarget) SUB=Subject; LSMESTIMATE trt*visit ' change at week 4c - AZD5718 vs placebo' -1 0 1 0 / cl ; RUN;

Distribution:

Original:

Copy:

TPCA025 Version 2 (based on TPQA036 Version 2)

Sponsor:	AstraZeneca AB	Protocol/CIP Number:	D7550C00003
CIL Project Number:	40343		

Where awtarget is the expected day of visit.

ANCOVA model – change at visit 4 on all variables except cardiovascular biomarkers at first Interim analysis:

The SAS code used to implement this test will be similar to that shown below:

PROC MIXED data=dataset; CLASS Trt MI; MODEL Ch= Trt MI Base; LSMESTIMATE trt ' change at week 4 – AZD5718 ng vs Placebo' -1 1 / cl ; RUN;

NB: LSMESTIMATE statement must be adapted based on data used in the model.

Distribution:

Original:

Copy:

TPCA025 Version 2 (based on TPQA036 Version 2) Effective Date: 27th August 2017 Prior Effective Date: 21st December 2016

Sponsor:	AstraZeneca AB	Protocol/CIP Number:	D7550C00003
CIL Project Number:	40343		

Appendix 3 Summary table of statistical models

ENDPOINT	Visit teste d	Data used	STATISTI CAL MODEL	TEST	ALPH A LEVE L	VARIABLE TRANSFO RMATION
Primary endpoint:		-A-				98
Change of Creatinine- normalised u-LTE4 at visit 4	4	2(B), 3,4, 4c	MMRM	Lower one-sided test of difference	0.05	Log-Normal
Secondary endpoint:						
First secondary endpoint						
Change of Creatinine- normalised u-LTE ₄ at visit 4c	4c	2(B), 3,4, 4c	MMRM	Lower one-sided test of difference	0.05	Log-Normal
Second secondary endpo	int					
Change of CFVR at visit 4c	4c	2(B), 4, 4c	MMRM	Upper one- sided test of difference	0.05	Log-Normal
Third secondary endpoin	ıt					-
Change of CFVR at visit	4	2(B), 4, 4c	MMRM	Upper one- sided test of difference	0.05	Log-Normal
All other secondary endp	oints				P.	
Change in: • LAD resting mean diastolic flow velocity • LAD hyperaemic flow velocity • LV ejection fraction (LVEF) at rest • LV Global Longitudinal Strain (GLS) at rest and at hyperaemia • LV Global Circumferential Strain (GCS) at rest • LV longitudinal early diastolic strain rate	4	2(B), 4, 4c	MMRM	Two-sided test of difference	0.05	Normal / Log-Normal depending on Q-Q plots.

Distribution:

Original:

Copy:

Sponsor:	AstraZeneca AB	Protocol/CIP Number:	D7550C00003
CIL Project Number:	40343		

ENDPOINT	Visit teste d	Data used	STATISTI CAL MODEL	TEST	ALPH A LEVE L	VARIABLE TRANSFO RMATION
Exploratory endpoints:		\$				98
Change in: • LAD resting mean diastolic flow velocity • LAD hyperaemic flow velocity • LV ejection fraction (LVEF) at rest • LV Global Longitudinal Strain (GLS) at rest and at hyperaemia • LV Global Circumferential Strain (GCS) at rest • LV longitudinal early diastolic strain rate	4c	2(B), 4, 4c	MMRM	Two-sided test of difference	0.05	Normal / Log-Normal depending on Q-Q plots.
Change in Carotid- femoral pulse wave velocity and brachial pulse wave analysis (cfPWV/bPWA): • Augmentation index, • Carotid-femoral pulse wave velocity, • Pulse pressure amplification, • Central pulse pressure, • Central pulse pressure systolic/diastolic, • Brachial blood pressure systolic/diastolic	4	2(B), 4, 4c	MMRM	Two-sided test of difference	0.05	Normal / Log-Normal depending on Q-Q plots.
Change in Carotid- femoral pulse wave velocity and brachial pulse wave analysis (cfPWV/bPWA): • Augmentation index, • Carotid-femoral pulse wave velocity, • Pulse pressure amplification,	4c	2(B), 4, 4c	MMRM	Two-sided test of difference	0.05	Normal / Log-Normal depending on Q-Q plots.

Distribution:

Original:

Copy:

TPCA025 Version 2 (based on TPQA036 Version 2)

Sponsor:	AstraZeneca AB	Protocol/CIP Number:	D7550C00003	
CIL Project Number:	40343			

ENDPOINT	Visit teste d	Data used	STATISTI CAL MODEL	TEST	ALPH A LEVE L	VARIABLE TRANSFO RMATION
 Central pulse pressure, Central blood pressure systolic/diastolic, Brachial blood pressure systolic/diastolic 						
Change in Clinical Outcome Assessments: • SF-36 • EQ-5D • Rose Dyspnoea score • FACIT-Fatigue	4	2(B), 4, 4c	MMRM	Two-sided test of difference	0.05	Normal
Change in Clinical Outcome Assessments: • SF-36 • EQ-5D • Rose Dyspnoea score • FACIT-Fatigue	4c	2(B), 4, 4c	MMRM	Two-sided test of difference	0.05	Normal

Exploratory cardiovascular biomarker:

Change in: • Total cholesterol • Low density lipoprotein cholesterol (LDL-C) • High density lipoprotein cholesterol, (HDL-C) • Triglycerides • hsTnI (high sensitive Troponin I) • hsCRP (High- sensitivity C-Reactive Protein) • NT-proBNP (N- Terminal Prohormone of Brain Natriuretic Peptide) • Lp(a) (Lipoprotein a) • ApoA1 (Apolipoprotein A) • ApoB	4	2(B), 3, 4, 4c	MMRM	Two-sided test of difference	0.05	Normal / Log-Normal depending on Q-Q plots.
---	---	----------------	------	------------------------------------	------	---

Distribution:

Original:

Copy:

TPCA025 Version 2 (based on TPQA036 Version 2) Effective Date: 27th August 2017 Prior Effective Date: 21st December 2016

Sponsor:	AstraZeneca AB	Protocol/CIP Number:	D7550C00003	
CIL Project Number:	40343			

ENDPOINT	Visit teste d	Data used	STATISTI CAL MODEL	TEST	ALPH A LEVE L	VARIABLE TRANSFO RMATION
Change in: • Total cholesterol • Low density lipoprotein cholesterol (LDL-C) • High density lipoprotein cholesterol, (HDL-C) • Triglycerides • hsTnI (high sensitive Troponin I) • hsCRP (High- sensitivity C-Reactive Protein) • NT-proBNP (N- Terminal Prohormone of Brain Natriuretic Peptide) • Lp(a) (Lipoprotein a) • ApoA1 (Apolipoprotein A) • ApoB	4c	2(B), 3, 4, 4c	MMRM	Two-sided test of difference	0.05	Normal / Log-Normal depending on Q-Q plots.

First Interim analysis

Change of CFVR at visit 4	4	2(B), 4	ANCOVA	Two-sided test of difference	0.05	Log-Normal
Change of LV-GLS at rest at visit 4	4	2(B), 4	ANCOVA	Two-sided test of difference	0.05	Normal / Log-Normal depending on Q-Q plots.
Change of LVEF at rest at visit 4	4	2(B), 4	ANCOVA	Two-sided test of difference	0.05	Normal / Log-Normal depending on Q-Q plots.
Change in Carotid- femoral pulse wave velocity and brachial pulse wave analysis (cfPWV/bPWA): • Augmentation index, • Carotid-femoral pulse	4	2(B), 4	ANCOVA	Two-sided test of difference	0.05	Normal / Log-Normal depending on Q-Q plots.

Distribution:

Original:

Copy:

Effective Date: 27th August 2017 Prior Effective Date: 21st December 2016

Sponsor:	AstraZeneca AB	Protocol/CIP Number:	D7550C00003	
CIL Project Number:	40343			

ENDPOINT	Visit teste d	Data used	STATISTI CAL MODEL	TEST	ALPH A LEVE L	VARIABLE TRANSFO RMATION
wave velocity, • Pulse pressure amplification, • Central pulse pressure						
Change in Cardiovascular biomarkers: • hsCRP (High- sensitivity C-Reactive Protein) • NT-proBNP (N- Terminal Prohormone of Brain Natriuretic Peptide)	4	2(B), 3, 4	MMRM	Two-sided test of difference	0.05	Normal / Log-Normal depending on Q-Q plots.

Second Interim analysis

Change of CFVR at visit 4	4	2(B), 4, 4c	MMRM	Two-sided test of difference	0.05	Log-Normal
Change of CFVR at visit 4c	4c	2(B), 4, 4c	MMRM	Two-sided test of difference	0.05	Log-Normal
Change of LAD hyperaemic flow velocity at visit 4	4	2(B), 4, 4c	MMRM	Two-sided test of difference	0.05	Normal / Log-Normal depending on Q-Q plots.
Change of LAD hyperaemic flow velocity at visit 4c	4c	2(B), 4, 4c	MMRM	Two-sided test of difference	0.05	Normal / Log-Normal depending on Q-Q plots.
Change of LV-GLS at rest at visit 4	4	2(B), 4, 4c	MMRM	Two-sided test of difference	0.05	Normal / Log-Normal depending on Q-Q plots.
Change of LV-GLS at rest at visit 4c	4c	2(B), 4, 4c	MMRM	Two-sided test of difference	0.05	Normal / Log-Normal depending on Q-Q plots.

Distribution:

Original:

Copy:

TPCA025 Version 2 (based on TPQA036 Version 2)

Sponsor:	AstraZeneca AB	Protocol/CIP Number:	D7550C00003	
CIL Project Number:	40343			

ENDPOINT	Visit teste d	Data used	STATISTI CAL MODEL	TEST	ALPH A LEVE L	VARIABLE TRANSFO RMATION
Change of LVEF at rest at visit 4	4	2(B), 4, 4c	MMRM	Two-sided test of difference	0.05	Normal / Log-Normal depending on Q-Q plots.
Change of LVEF at rest at visit 4c	4c	2(B), 4, 4c	MMRM	Two-sided test of difference	0.05	Normal / Log-Normal depending on Q-Q plots.
Change in Cardiovascular biomarkers: • hsCRP (High- sensitivity C-Reactive Protein) • NT-proBNP (N- Terminal Prohormone of Brain Natriuretic Peptide)	4	2(B), 3, 4, 4c	MMRM	Two-sided test of difference	0.05	Normal / Log-Normal depending on Q-Q plots.
Change in Cardiovascular biomarkers: • hsCRP (High- sensitivity C-Reactive Protein) • NT-proBNP (N- Terminal Prohormone of Brain Natriuretic Peptide)	4c	2(B), 3, 4, 4c	MMRM	Two-sided test of difference	0.05	Normal / Log-Normal depending on Q-Q plots.

Distribution:

Original:

Copy:

TPCA025 Version 2 (based on TPQA036 Version 2) Effective Date: 27th August 2017 Prior Effective Date: 21st December 2016

OTATIOTICAL ANALVOID DI AN

Sponsor:	AstraZeneca AB	Protocol/CIP Number:	D7550C00003
CIL Project Number:	40343		÷
12. TABLE	SHELLS AND S	PECIFICATIONS	
14. SUMMARY TABLES AND FIGURE	S LISTINGS AND NARRATIVES		
14.1 Demographic, baseline, concorr	where we do not not not the	-specific characteristics	
Table 14.1.1 - Subjects disposition - Co	In the second		
Table 14.1.2 - Important protocol deviat			
Table 14.1.3 - Analysis sets			
Table 14.1.4 - Demographic characteris	stics (Efficacy Analysis Set)		
Table 14.1.5 - Demographic characteris	stics - Cohort 12 weeks treatment (Effi	cacy Analysis Set)	
Table 14.1.6 - Subject characteristics (I	Efficacy Analysis Set)		
Table 14.1.7 - Subject characteristics -	Cohort 12 weeks treatment (Efficacy /	Analysis Set)	
Table 14.1.8 - Relevant medical and su	rgical history (Efficacy Analysis Set)		
Table 14.1.9 - Specific medical and sur	gical history (Efficacy Analysis Set)		
Table 14.1.10 - All allowed concomitant	t medications during study treatment (Efficacy Analysis Set)	
Table 14.1.11 - Study treatment compli	ance - Cohort 4 weeks treatment and	Cohort 12 weeks treatment (Safety Analysis	Set)
Table 14.1.12 - Subject recruitment by	country and centre (Efficacy Analysis	Set)	
Table 14.1.13 - Stratification factors rec	corded at randomization by IRT - Coho	ort 4 weeks treatment and Cohort 12 weeks	treatment (Efficacy Analysis Set)
Table 14.1.14 - Nicotine use, categorise	ed (Efficacy Analysis Set)		
Table 14.1.15 - Alcohol use, categorise	d (Efficacy Analysis Set)		
